Exploratory quantitative analyses were conducted for 53 NHs (TB n=17, PB n=36 NHs). Primary resident-level outcomes included antipsychotic medication use, behavioral symptoms, wandering, and rejection of care, which were extracted from the Minimum Data Set and

electronic medical records. Six-month outcomes were captured prior to the emergence of COVID-19, while 12- and 18-month outcomes were after the start of the pandemic.

As a result of the COVID-19 pandemic and the significant impact it had on the study, the team bolstered the scope of the qualitative interviews from those that were originally planned. Qualitative data was collected via individual interviews with 327 NH staff (TB n=168, PB n=159) and 30 family caregivers (TB n= 13, PB n= 17) to explore their perspective of the two approaches as it relates to resident outcomes and training. Using mixed methods, quantitative and qualitative data were integrated to determine whether these sources confirm each other, provide emergent, or conflicting information.

Eligibility Criteria

Facility-level inclusion criteria required eligible NHs to (a) not have an existing dementia program targeting reduction of off-label antipsychotic medication use, (b) serve an average of >60 long-term care residents living with dementia, (c) be a CMS certified NH (e.g., conduct regularly scheduled resident assessments), and (d) comply with CMS's annual staff dementia care training requirement (i.e., 4 hours). Exclusion criteria included (a) NHs located in states that require more than four hours of dementia-specific training annually were excluded, (b) NHs that had existing dementia care programs which required staff to engage in additional training beyond the CMS minimum training requirements and more than the four hours required by the state.

Eligible NH residents included those that (a) have an existing diagnosis of ADRD or a Cognitive Function Scale score indicating Mild, Moderate, or Severe Cognitive Impairment, (b) are 65 years of age or older, and (c) are long-stay residents (>100 days). Post-acute care patients admitted for a brief stay (<100 days) and respite stay patients were excluded.

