where $Outcome_{ijt}$ is a binary variable of having the outcome measure of interest for resident j residing in NH i at time t . $Post$ is an indicator for being in the follow-up period after implementation of approaches, which would be 1 for $t=1$ and 0 for $t=0$. TB is an indicator for NH i , which would be 1 if assigned to team-based approach arm and 0 if assigned to problem-based approach arm. The comparative effectiveness (treatment effect) of the team-based approach relative to the problem-based approach would be estimated with β_2 , which is the coefficient estimate of $post_t \times TB_i$ representing residents in team-based approach NHs during the respective follow-up period while accounting secular time trends ($post_t$) and time invariant characteristics of NH using nursing home fixed effects (NH_i). In addition, the model accounts for a set of individual resident characteristics including age, sex, race/ethnicity, Cognitive Function Scale, number of valid assessments resident had for outcome during period (X_{ij}). Models were analyzed using complete case analysis. Standard errors were clustered at the NH level. Linear probability models were implemented for ease of interpretation; regression coefficients and standard errors are presented in percentage point units. Robustness checks were conducted by implementing logistic regression difference-in-differences models with NH characteristics rather than NH-level fixed-effects to estimate the treatment effect. Marginal effects from the logistic models were computed to complement the linear probability regression models.⁴⁰ Finally, stratified analyses were conducted to examine whether treatment effects were different among residents with moderate to severe dementia vs. mild dementia. All analyses were conducted using Stata 14.0 (Stata, College Station, TX).

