For resident-level primary and secondary outcomes, we conducted difference-in-differences analyses using baseline data and the first six months of post-implementation data (six-month outcomes; September 15, 2019 to March 14, 2020) to compare outcomes across the two study arms, prior to the emergence of the pandemic. Next, we conducted analyses of resident outcomes after the emergence of pandemic spanning post-implementation months (a) 7-12 (March 15, 2020-September 14, 2020) and (b) 13-18 (September 15, 2020-March 14, 2021) (12-month and 18-month outcomes analyses, respectively). Observations with missing resident covariates were excluded from the analyses.

For staff and resident secondary safety outcomes, we calculated the monthly rate (per 100 residents) of each outcome for each NH that submitted data each month. We averaged the

monthly measures available for each NH and then examined descriptive statistics (e.g., mean) to compare the outcomes across two arms during the first five months of implementation.

Qualitative Analysis

The objectives of the staff analyses were to explore (a) perceived barriers and facilitators surrounding the intervention approach, (b) perspectives on the training modules (e.g., adequacy, acceptability, satisfaction, burden), (c) the quality of resident-staff interactions (i.e., how staff training contributed to patient outcomes) and (d) training program recommendations for modifications (i.e., sustainability, scalability). We used a three-phase team-based rapid qualitative analysis approach.^{41,42} In phase one, interview transcripts were reviewed and summarized by domains (based on interview questions) and categories (emerging inductively) into a coding template. Phase two required reviewers to reduce, synthesize, and look for similarities and differences in the data through the use of matrices. In phase three, summary tabulation procedures occurred in which reviewers combined data (e.g., NH cases, care approaches), developing themes.⁴² We explored patterns and variations in themes within and across cases and care approaches.^{43,44}

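### The safety comparison averages whichever months each home submitted and does not align months between arms, so a difference in reporting pattern could pass for a difference in safety

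*Combined protocol and SAP*

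**What the plan says.** The safety analysis is described near the end of Statistical Considerations, just before Qualitative Analysis. Its unit is a home-month: "we calculated the monthly rate (per 100 residents) of each outcome for each NH that submitted data each month". The team then averaged the "monthly measures available for each NH and then examined descriptive statistics", naming the mean as an example, and set the two arms side by side on the results. The period covered is given as "during the first five months of implementation". This is the only analysis described for the staff and resident safety outcomes, which belong to Aim 2.

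The text gives no rule for months that were not submitted, no minimum number of months, no weights, no adjustment for calendar month, and no count of submitted months by arm. The missing-data statement elsewhere, "Models were analyzed using complete case analysis", belongs to the resident-level regression models and does not reach missing home-months. The difference-in-differences model, with its home fixed effects and clustered standard errors, is likewise specified for the resident-level outcomes.

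The resident-level follow-up uses the same dates for every home ("six-month outcomes; September 15, 2019 to March 14, 2020"). No dates are given for the safety window.

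**The concern.** The wording anticipates incomplete reporting, since rates exist only for homes and months with a submission. Averaging what is available within a home means that two homes can be summarised over different parts of the window. If that happens more in one arm, and if event rates drift over the window, the arm means describe different calendar periods. The contrast then mixes any effect of the care approach with the drift.

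At stake is how a reader interprets the safety half of Aim 2. Without a submission table, nobody outside the study team can tell whether a lower arm mean reflects fewer events or a different set of months.

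**Working it through.** The plan states no safety rate, event count or submission count, so there is no figure to reproduce. From the documents: a five-month window; 17 team-based (TB) and 36 problem-based (PB) homes (Study Design & Methods); homes with "serve an average of >60 long-term care residents living with dementia", which is the source of the 60 residents used in step 5. **All rates and submission patterns below are assumptions.**

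**1. Size of the calendar effect.** Let both arms share the same monthly rates r1 to r5, so the true arm difference is zero. If a share f of TB homes reports only months 1 and 2, then

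TB mean = (1 - f) × mean(r1..r5) + f × mean(r1, r2).

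With rates 4, 4.5, 5, 5.5, 6 per 100 and f = 0.5: 0.5 × 5.0 + 0.5 × 4.25 = 4.625. With PB complete at 5.0, TB - PB = **-0.375**. If half the PB homes report only months 4 and 5, the PB mean is 0.5 × 5.0 + 0.5 × 5.75 = 5.375 and the difference is -0.75.

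| Assumed trend per 100 | Half of TB early only, PB complete | Half of TB early only, half of PB late only |
|---|---|---|
| flat at 5 | 0 | 0 |
| 4.5 to 5.5 | -0.19 | -0.375 |
| 4 to 6 | -0.375 | -0.75 |
| 3 to 7 | -0.75 | -1.5 |

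**2. Direction.** With the 4-to-6 trend, if half the TB homes instead report only months 4 and 5 and PB is complete, TB - PB = 5.375 - 5.0 = +0.375. The same rule can suggest benefit or harm.

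**3. What removes it.** Weighting homes by months submitted only shrinks it: (0.5 × 5 × 5.0 + 0.5 × 2 × 4.25) / (0.5 × 5 + 0.5 × 2) = 16.75 / 3.5 = 4.786, a difference of -0.214. With month indicators it goes to 0. In this example the rate depends on month alone, so a model with arm and month terms fits exactly with an arm coefficient of zero, whatever positive weights are used. This requires that the arms share months and that the month pattern is common to both.

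**4. Should homes that report more count more?** Suppose 2/7 of homes run at 15 per 100 and submit each month with probability 0.5, and 5/7 run at 8 and submit with probability 0.9. The true home-equal mean is 2/7 × 15 + 5/7 × 8 = 10.0.

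- Mean of home averages (homes with at least one month): [2/7 × (1 - 0.5^5) × 15 + 5/7 × (1 - 0.1^5) × 8] / [2/7 × (1 - 0.5^5) + 5/7 × (1 - 0.1^5)] = 9.866 / 0.991 = **9.95**.
- Pooled home-months, as a count model with a resident offset would weight them: (2/7 × 0.5 × 15 + 5/7 × 0.9 × 8) / (2/7 × 0.5 + 5/7 × 0.9) = 7.286 / 0.786 = **9.27**.
- Homes with all five months: (2/7 × 0.5^5 × 15 + 5/7 × 0.9^5 × 8) / (2/7 × 0.5^5 + 5/7 × 0.9^5) = 3.508 / 0.431 = **8.15**.

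Here the plan's equal weighting is closest to the truth. If instead the high rate belongs to a month rather than a home, with months independent, all three give 9.27 against 10.0. Restricting to complete reporters would then agree with the biased answer.

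**5. Precision.** Assume Poisson counts, 5 events per 100 per month and 60 residents. The sampling variance of a home's rate is 5/100/60 × 10^4 = 8.33 for one month and 1.67 for five. Let 8 of the 17 TB homes submit one month and 9 submit five. With between-home SD 1 per 100, the standard error of the TB mean is 0.58 with equal weights and 0.49 with month weights. With SD 3 it is 0.90 and 0.95. Neither weighting is always more precise.

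**The case against.** The strongest reply is that nothing here is shown to have happened. No submission pattern is reported. If rates were flat, or the arms submitted alike, the problem disappears. The calendar effect is also bounded: if the safety window starts on the resident-level date of 15 September 2019, five months end on 14 February 2020, before the pandemic period that the plan dates from 15 March 2020. The outcomes are secondary, the analysis is expressly exploratory, the comparison is descriptive, and no test or safety conclusion is specified. The text is also open that it uses submitted and available months. All of this stands, and it limits the point to a possible bias with an inexpensive remedy.

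The reply also holds on weighting. Homes were randomised, so a mean that counts each home once is a proper cluster-level summary. A reader might infer that letting a one-month home count as much as a five-month home is itself an error. Steps 4 and 5 do not support that.

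The reply does not answer the alignment question. Nothing in the documents ensures that the two arms are compared over the same months, and nothing lets a reader see whether they were.

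**Conclusion.** The point holds as a gap in month alignment and in the visibility of reporting. On the assumed 4-to-6 trend with half the TB homes reporting only the first two months, the stated rule yields -0.375 per 100 with no true effect. The range is 0 to -0.75 over the trends tried with PB complete, double that if half the PB homes report only late months, and the sign reverses if TB homes report late. Two conditions are needed together: rates that change within the window, and submission that differs by arm. The documents establish neither.

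A reader might go further and infer that under-reporting is being turned into an apparent safety benefit. The documents do not support this. A month that was not submitted has no rate and is not counted as zero events. It lowers a home's average only if it would have been worse than that home's other months, and it biases the comparison only if this differs by arm. Events left out of a submitted month are a separate problem that no choice of weights addresses.

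**What to change.** - Keep the mean of home averages as the descriptive summary.
- Base the arm comparison on home-month rates, with indicators for arm and calendar month. Weight each home-month by 1/(months that home submitted), so that each home still counts once, and cluster standard errors by home.
- Tabulate submitted home-months by arm and calendar month, and state the calendar dates of the safety window.
- Do not state that one approach is safer if submission differs by arm and the month-adjusted comparison disagrees with the unadjusted one.
- A count model with a resident offset may be added as a sensitivity analysis only, because it favours homes that report more.
- Say plainly that neither the count model nor an analysis of complete reporters removes bias from months missed because of bad events.

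The cost is SAP wording, one table, and one slightly more complex model for each secondary, exploratory outcome. The home-month rates have already been calculated, so no new data are needed.

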The initial study protocol was designed and initiated prior to the emergence of the COVID-19 pandemic. However, with the emergence of the COVID-19 pandemic, our study was modified to also include looking at the impact of the pandemic. Thus, two questions were addressed by this study: (a) is there a statistically significant difference in resident outcomes among NH residents living with dementia based on the non-pharmacological approach to dementia care? And (b) How did these non-pharmacological approaches compare after the emergence of COVID-19 when residents and staff faced social isolation, infection control policies, and staffing shortages? These questions were addressed via three aims:

Aim 1: Compare the effectiveness of two non-pharmacological approaches for dementia care (*TB and PB*) in reducing the use of antipsychotic medications and behavioral and psychological symptoms in NH residents living with dementia.

Aim 2: Determine the effectiveness of the two non-pharmacological approaches on NH residents living with dementia and staff safety and wellness.

Aim 3: Identify benefits, limitations, barriers, and facilitators of each approach from the perspectives of the NH staff and NH residents' families. This qualitative data will augment the resident-level quantitative data by more fully capturing the impact of the two approaches on resident outcomes; resident-staff, staff-family, and resident-family interactions; and staff job roles before and after the emergence of COVID-19, which will guide future implementation.

Study Design & Methods

The study was initiated in January 2018. As of March 2020, 80 NHs had been recruited, randomized and staff training delivered. The COVID-19 pandemic emerged in early March 2020. Subsequent national lockdown of NHs and leadership requests to not communicate with the NHs as they navigate the early days of the pandemic resulted in a pause on all research related communication between the study team and study sites.

As the pandemic evolved, the study team developed a plan for moving forward, which included assessing the ability for NHs to re-engage in the study. Due to the negative impact of the pandemic, 27 of the 80 NHs were unable to re-engage. The remaining 53 NHs were included in the revised study protocol. This change resulted in the original cluster randomized control trial becoming two sets of exploratory analyses differentiated by the emergence of the COVID-19 pandemic.

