Eligible staff were employed by a participating NH and included all staff categories, (a) professional healthcare providers, including licensed staff with professional degrees, such as registered nurses, licensed practical nurses, rehabilitation practitioners (e.g., occupational [OT], physical [PT], speech therapists [SLP]), certified therapeutic recreation specialist, dieticians, (b) direct care providers such as certified nursing assistants [CNA], activities department staff, nutrition services personnel (e.g., dining services/aids); (c) ancillary support staff, including environmental services workers (e.g., maintenance, housekeeping, kitchen staff) and administrative staff (e.g., reception, billing department, medical records); and (d) administrators, including executive directors, directors of nursing.

Eligible family caregivers were the primary contact for a resident living with dementia in a participating NH (e.g., relative, spouse, partner, friend, per neighbor).

Statistical Considerations

Descriptive analyses included calculating appropriate central tendencies (e.g., mean) for each outcome variable. We examined outcomes separately before and after the emergence of COVID-19. To assess validity of randomization, we compared resident characteristics and outcomes and NH characteristics by arm for the six-month baseline period prior to training (December 16, 2018 to June 15, 2019).

We used the intention-to-treat analytic approach to conduct the exploratory quantitative analysis. A difference-in-differences analytic model was used, rather than comparing outcomes across the arms during each six-month period after the training, to account for baseline differences in resident characteristics and outcomes. The estimating equation is as follows:

$$Outcome_{ijt} = \beta_0 + post_t\beta_1 + (post_t \times TB_i)\beta_2 + X_{ij}\delta + NH_i + u_{ijt}$$

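### The Aim 2 safety rates are compared between arms in follow-up only and without baseline adjustment, so any pre-existing difference between the reporting homes would be carried into the comparison

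*Combined protocol and SAP*

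**What the plan says.** The combined protocol and SAP treats two groups of outcomes differently within its Statistical Considerations.

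- **Modelled resident outcomes.** A difference-in-differences model is used, with home fixed effects and resident covariates. It was chosen "rather than comparing outcomes across the arms during each six-month period after the training, to account for baseline differences in resident characteristics and outcomes".
- **Staff and resident safety outcomes.** These are secondary outcomes: "we calculated the monthly rate (per 100 residents) of each outcome for each NH that submitted data each month". Each home's available monthly figures are then averaged, and descriptive summaries such as means serve "to compare the outcomes across two arms during the first five months of implementation". No baseline window, covariate, home effect, standard error, interval or test is described.

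Aim 2, under Study Objectives, is to "Determine the effectiveness of the two non-pharmacological approaches on NH residents living with dementia and staff safety and wellness".

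On the homes available, Study Design & Methods says that "27 of the 80 NHs were unable to re-engage" after the pandemic began, and that "Exploratory quantitative analyses were conducted for 53 NHs (TB n=17, PB n=36 NHs"). The quantitative analyses are called exploratory. Characteristics and outcomes were compared by arm for a six-month baseline (December 16, 2018 to June 15, 2019). That comparison is a check on randomization and not an adjustment, and safety rates are not named in it.

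**The concern.** The reason the plan gives for adjusting the modelled resident outcomes is that the arms may have differed at baseline. That reason does not stop at those outcomes. Homes with more severely impaired residents, or with more events before training, can be expected to report more events afterwards whichever approach they were assigned. A comparison of follow-up means alone cannot separate that history from the approach.

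Randomization gives limited protection here. A third of the randomized homes were lost, the loss by arm is not stated, and the remaining split is 17 to 36. The safety comparison may rest on fewer homes still, because only those that submitted data contribute.

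What is at stake is the safety part of Aim 2. An unadjusted gap could be taken for an effect of one approach, or a real effect could be masked by an opposite baseline gap.

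**Working it through.** **Inputs from the documents.** 80 homes randomized, 27 lost, 17 TB and 36 PB analysed. No safety rate, SD, between-arm difference, alpha, power or count of safety-reporting homes is given. Results below are therefore in units of the between-home SD of the five-month average rate.

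**Count check.** 80 − 27 = 53 and 17 + 36 = 53. The plan's figure is reproduced.

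**Precision of the raw comparison.** With n₁ and n₂ homes, the SE of a difference in home means is √(1/n₁ + 1/n₂) SD.

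| Reporting homes (TB, PB) | SE (SD) | 95% chance range (1.96 × SE) |
|---|---|---|
| 17, 36 (all homes report) | 0.294 | ±0.58 SD |
| 12, 25 (assumed) | 0.351 | ±0.69 SD |
| 8, 18 (assumed) | 0.425 | ±0.83 SD |

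The first row is the best case. These ranges describe chance imbalance with no treatment effect and no selection.

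**Can balance be assumed?** The original allocation is not stated. If it was 40:40, retention was 17/40 = 42.5% in TB and 36/40 = 90% in PB. If it was 27:53, retention was 17/27 = 63% and 36/53 = 68%, close to equal. The documents do not settle which, so balance can be neither assumed nor ruled out.

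**What adjustment would gain.** If baseline covariates explain a share R² of between-home variance, the SE is multiplied by √(1 − R²). All R² values are assumptions.

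| R² | √(1 − R²) | SE with 17 and 36 homes | Reduction |
|---|---|---|---|
| 0.10 | 0.949 | 0.279 | 5% |
| 0.25 | 0.866 | 0.255 | 13% |
| 0.50 | 0.707 | 0.208 | 29% |

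**What a baseline gap would carry forward.** A gap of g SD in a baseline measure that correlates r with the follow-up rate shifts the raw difference by r × g. For a single covariate r = √R², so R² of 0.10 to 0.50 gives r of about 0.32 to 0.71. A gap of one SE (0.294 SD) then shifts the raw difference by 0.294 × 0.316 = 0.09 SD to 0.294 × 0.707 = 0.21 SD.

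**Cost in degrees of freedom.** A two-arm comparison of 53 homes leaves 53 − 2 = 51. Two or three covariates leave 49 or 48, and fewer if reporting was partial.

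**The case against.** The strongest reply is that the plan claims little for these outcomes. They are secondary, the summary is descriptive, no test or coefficient is stated, and the term treatment effect is kept for the model coefficient. Baseline safety rates may never have been collected, in which case difference-in-differences was not possible and the different handling reflects the data rather than inconsistency. The ±0.58 SD range is ordinary sampling error, which an interval would convey; it is not bias.

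Much of this stands. A reader might infer that the TB and PB homes are known to have differed in safety before training, and that the reported gap is that difference. The documents do not support this: they contain no safety rate at any time, and the baseline differences they mention arise in introducing the resident-level model.

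A reader might also take a 0.5 SD baseline gap and a correlation of 0.7 and conclude that the false difference is 0.35 SD. That gap is 0.5/0.294 = 1.7 standard errors, which chance alone produces or exceeds about 9% of the time. A correlation of 0.7 is most natural for a home's own earlier safety rate, which may not exist; nothing in the documents shows that behavioral symptoms or cognitive status predict safety rates so strongly.

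The reply does not dispose of the point. The modelled outcomes are equally exploratory and were adjusted. The stated purpose of the safety summary is to compare arms, and Aim 2 asks about effectiveness. Lack of baseline safety rates rules out difference-in-differences but not adjustment for other baseline measures.

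**Conclusion.** The point holds as a gap in the analysis. The safety comparison is follow-up only and unadjusted, which is the design the plan itself sets aside for its modelled resident outcomes, and nothing elsewhere in the documents corrects for this.

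Whether an imbalance in safety exists, and in which direction, cannot be determined from the documents. Chance alone allows a gap of about ±0.58 between-home SDs with all 53 homes reporting, and more with partial reporting. The gain from adjustment is modest to useful, a 5 to 29% smaller standard error, and rests wholly on the assumed 10 to 50% of variance explained.

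This is a change that should be made to an exploratory secondary analysis. It does not show that the safety results are wrong.

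**What to change.** Keep the raw arm means and add beside them one home-level regression per safety outcome, with the home's average rate as the response and arm as the factor of interest.

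- **Covariates.** Use two or three measures from the December 2018 to June 2019 baseline that the team already holds, such as prevalence of behavioral symptoms and the share of residents with moderate to severe impairment on the Cognitive Function Scale. Add the home's own pre-implementation safety rate where it exists, and state whether such rates were collected.
- **Reporting.** Give the adjusted difference with an interval based on between-home variation, and the number of reporting homes and reporting months by arm.
- **Interpretation.** Draw any Aim 2 safety statement from the adjusted estimate and label it exploratory. Label the raw means as unadjusted.

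The cost is one regression per outcome on baseline data in hand, and two or three of at most about 51 home-level degrees of freedom. The relative cost rises if few homes reported, so the number of covariates should be fixed with the reporting counts in view and before the safety rates are compared by arm. Adjustment does not remove selection arising from homes that did not report, which is why the reporting counts belong beside the estimate.
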